Study of the Efficacy of 532nm Laser and 1064 nm Laser in the Treatment of
Cutaneous Lupus Erythematosus Versus Topical Corticosteroids Alone

NCT03639857

Date: May 22nd, 2019

1) Protocol Title

A Comparative Study of the Efficacy of 532nm Laser and 1064 nm laser as Adjuncts to Topical Corticosteroids in the Treatment of Cutaneous Lupus Erythematosus Versus Topical Corticosteroids Alone

2) Principal Investigator

[name] M.D., UCF College of Medicine, UCF Health

Co-Principal Investigator: [name] M.D., UCF Health

Co-Principal Investigator: [name] B.S., UCF College of Medicine

Co-Principal Investigator: [name] B.A., UCF College of Medicine

Co-Principal Investigator: [name], B.S., UCF College of Medicine

Co-Principal Investigator: [name], B.S., UCF College of Medicine

Sub-Investigator: [name], B.A., UCF College of Medicine

Sub-Investigator: [name], B.A., UCF College of Medicine

3) Objectives

This study aims to compare the efficacy of 532nm Potassium Titanyl Phosphate (KTP) laser and 1064 nm Neodymium-doped Yttrium Aluminum Garnet (Nd:YAG) laser as adjuncts to topical corticosteroids in the treatment of cutaneous lupus erythematosus versus topical corticosteroids alone.

Our hypothesis is that adding laser treatment to standard of care will result in quicker resolution of lesions of cutaneous lupus. Furthermore we hypothesize that the 532nm laser will be more effective than the 1064nm laser.

The results of the study will either be submitted for publication in a journal or presented at a conference. Data from this study also could be used for further studies to clarify the ideal laser settings for use in cutaneous lupus.

4) Background

Systemic Lupus Erythematosus (SLE) is an autoimmune disorder characterized by the production of autoantibodies that can affect almost every organ in the human body. Most commonly there is a skin and musculoskeletal involvement, but there also can be hematologic, renal, and central nervous system manifestations as well.¹

It is estimated that 80% of people with SLE have skin involvement referred to as Cutaneous Lupus Erythematosus (CLE). CLE can develop independently of SLE and is more prevalent than SLE alone. Women ages 20 to 50 years old are most commonly affected by CLE although males and other ages can be affected as well.²

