- Research will be conducted during [name] clinical time. [name], a UCF Health board-certified physician, will perform the screening of eligible participants. [name] has significant prior experience conducting research, knowledge of the regulations and customs at UCF Health, and works regularly with patients performing laser treatments. Off-label laser treatments currently performed are fractionated CO2 laser for morphea, 1064nm and 532nm laser for sarcoidosis and acne, and 532nm laser for cutaneous lupus among others. Experience has been presented at invited talks/grand rounds. All treatments will be administered by [name].
- All individuals assisting in the research study will be provided a copy of the approved IRB study protocol and given the opportunity to meet with the principal investigator before recruitment begins. The principal investigator, [name], will be responsible for informing all research staff of their research-related duties during a personal meeting or via phone or email. The contact information of the principal investigator and co-principal investigators will be distributed to all research staff and the participants.

- The study will be conducted at the UCF Health Clinic, see section 5 (Setting of the Human Research). Extramural funding will be sought from various organizations or industry.
- The chances of a research related injury are extremely rare. However treatment for research related minor injuries will be made available at no cost by [name] if possible. For injuries that cannot be treated by [name] the participant will be referred elsewhere. Costs associated with this treatment may be billed to the participant's insurance company. Costs not covered by participant's insurance company will be the participant's responsibility.
- The study has been approved by the UCF Health Privacy Officer.

7) Study Design

a) Recruitment Methods

- For this study, we will recruit 25 adult male and female volunteers age 18 years and older. This number was calculated with the University of California San Francisco (UCSF) Clinical and Translational Science Institute Sample Size Calculator with a power of 0.8, effect size of 0.25, and alpha of 0.05.

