 - Unable to read and speak English since consent will only be available in English

[figure not shown]
- d) Study Endpoints
 - Primary endpoints: Participation in the study will end after the third visit.
 - Primary safety endpoints: none
 - Secondary safety endpoints:
 - Adverse reaction to the laser treatment such as blister, ulceration, and scarring.
 - Adverse reaction to the topical steroid such as atrophy, telangiectasias or striae.
 - Intolerance to pain of laser procedure.

- e) Study Timelines
 - Each participant will be in the study for a maximum of 8 weeks. Participants will receive 2 laser treatments. The laser treatments will be spaced 4 weeks apart between visit 1 and visit 2. Finally, 4 weeks after visit 2, the participants will be followed up during visit 3.

 - The duration expected for all study participants to be recruited is estimated to be 28 weeks.

 - The study will end when the last participant has completed the 2 laser treatments and follow up. The goal is to conclude the data collection by October 31, 2018 and complete primary analysis by December 31, 2018.

- f) Procedures involved in the Human Research.
- This study will be a randomized prospective study. All study lesions will receive topical treatment. One lesion will only receive topical treatment to serve as a control, and up to 2 others will also receive laser treatment in addition to the topical treatment.
 - Standard of care treatment will be a topical corticosteroid as follows:
 - Discoid lupus lesions: Betamethasone dipropionate augmented 0.05% cream twice a day as needed
 - Non-discoid cutaneous lupus lesions: Triamcinolone acetonide 0.1% cream twice a day as needed
 - Laser treatment will be randomized based upon the participant Fitzpatrick Skin Type as follows:
 - Fitzpatrick Skin Types I – III:
 - § Treatment lesion will be treated with 532nm laser or 1064nm laser
 - § 50:50 randomization for laser used (determined by coin flip)
 - § If the participants have an additional lesion then this will be treated with the laser not used for the treatment lesion
 - Fitzpatrick Skin Types IV - VI
 - § Treatment lesion will only be treated with the 1064nm laser. This is because the 532 nm wavelength is absorbed easily by melanin and thus can cause skin pigmentation abnormalities when used with darker skin participants.
 - Laser treatment system details and parameters:

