g) Data and specimen management

There will be no specimen collection, and thus there will be no management of physical specimens.

If a participant withdraws from the study, the reason for the withdrawal will be noted but data collected up to that point will be used.

All data will be collected on the survey documents (see attached documents “Survey” and “Independent Observer Survey”). These survey documents will be stored in regulatory binder in a locked drawer in locked room at UCF Health. This will only be accessible only to the principal investigator and co-principal investigators. These survey documents will then be used to transfer the data to the REDCap database, afterwards they will be disposed of in HIPAA-compliant shred bin.

Photographs of study lesions will be stored directly in the EHR.

The data will be analyzed for significant differences with aid of a statistician. A significance level of 0.05 will be used for statistical hypothesis testing. The results of the data analysis will be graphed for each parameter.

h) Provisions to monitor the data for the safety of participants

The principal investigator and statistician will periodically review cumulative CLASI scores and adverse effect data every 10 patients.

If the change in the active CLASI score for the treatment lesion is 3 points higher than the change in the active CLASI score for control lesions with $p < 0.05$ then the study will be suspended immediately.

If participants have ulceration or scarring attributable to the laser treatment as an adverse effect with $p < 0.05$ then the study will be suspended immediately.

i) Withdrawal of participants

Participants will be withdrawn from the research without their consent if they become intolerant to the laser treatments and/or the investigators determine that they are too nervous, anxious to continue.

Participants may terminate their participation in the research study at any time by informing a member of the research team. If the participant declines any further laser treatments he or she may still participate in the study with follow up assessments being completed.

If participants miss study Visit 2, the researchers will attempt to reach the participant to reschedule. If the participant is unable to reschedule within 2 weeks of the missed appointment then the participant will forego the 2nd treatment and attempted to be scheduled for Visit 3.

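### The primary-endpoint line states when participation ends, and nothing else in the plan selects the score, assessor, visit or contrast for the scheduled primary analysis

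*Combined protocol and SAP*

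**What the plan says.** All places are in the combined protocol and SAP.

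- **Section 7d (Study Endpoints)**: "Primary endpoints: Participation in the study will end after the third visit". The entries that follow concern safety only.
- **Section 7e (Study Timelines)**: "The goal is to conclude the data collection by October 31, 2018 and complete primary analysis by December 31, 2018". The content of that analysis is not given there or elsewhere.
- **Section 3 (Objectives)**: two hypotheses. The first is that "adding laser treatment to standard of care will result in quicker resolution of lesions of cutaneous lupus"; the second is that 532 nm outperforms 1064 nm. They are not ranked.
- **Section 7a (Recruitment Methods)**: 25 participants, calculated "with a power of 0.8, effect size of 0.25, and alpha of 0.05". No outcome, contrast or standard deviation is given.
- **Section 7f (Lesion assessment)**: active (0-5), damage (maximum 3) and total (0-8) limited CLASI, assessed at weeks 0, 4 and 8. There is one in-person evaluator and one photograph evaluator. Only the second is described as blinded to treatment type. A cosmetic VAS is also collected. None of these is called primary.
- **Section 7g (Data and specimen management)**: "The data will be analyzed for significant differences with aid of a statistician. A significance level of 0.05 will be used for statistical hypothesis testing". Then: "The results of the data analysis will be graphed for each parameter".
- **Section 7h (safety monitoring)**: "The principal investigator and statistician will periodically review cumulative CLASI scores and adverse effect data every 10 patients". A suspension rule begins "If the change in the active CLASI score for the treatment lesion is 3 points higher than the change in the active CLASI score" and compares the treatment lesion with control lesions at p<0.05.

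**The concern.** A 5% significance level has its usual meaning only if the test was chosen without knowledge of the results. Here the plan schedules a primary analysis and a testing level but leaves four choices open: score, assessor, visit and contrast. Someone following it faithfully could report whichever combination reaches p<0.05.

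Two features add to this. The plan obtains a blinded photograph assessment but gives it no priority, so an efficacy claim could rest on the in-person score alone and lose the protection against observer bias that the blinded reading offers. Cumulative CLASI scores are also reviewed every 10 patients, that is at 10 and 20 of 25, by the principal investigator and the statistician. An endpoint named late could therefore be named after results had been seen.

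**Working it through.** **1. Does the sample-size sentence point to a hidden primary outcome?** Inputs from section 7a: effect size 0.25, power 0.8, alpha 0.05, N = 25. Read as a standardised within-participant difference, n = ((z_alpha + z_power)/d)².
- Two-sided: ((1.960 + 0.842)/0.25)² = 125.6, so 126.
- One-sided: ((1.645 + 0.842)/0.25)² = 98.9, so 99.
- Two independent groups, two-sided: 252 per arm.

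None gives 25. About 25 appears only with inputs that the plan does not state, such as a raw difference of 0.25 with SD 0.5, paired and one-sided. The sentence therefore identifies no outcome or contrast. Whether 25 is adequate is a separate matter.

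**2. Does any other text select the test?**

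| Section | Score | Assessor | Visit | Contrast |
|---|---|---|---|---|
| 3 | resolution, with no variable defined | no | no | two, unranked |
| 7d primary line | no | no | no | no |
| 7e primary analysis | no | no | no | no |
| 7f assessments | three CLASI scores, VAS | two | weeks 4 and 8 | no |
| 7g testing | every parameter | no | no | no |
| 7h suspension rule | active CLASI change | no | no | treatment v control lesion |

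Section 7h comes closest. It is a safety rule, and it leaves assessor and visit open.

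**3. How large could the effect on the error rate be?** For k independent tests the chance of at least one p<0.05 under no effect is 1 − 0.95^k:
- k = 2: 0.0975
- k = 4: 0.185
- k = 12: 0.460

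The tests here share participants and lesions, so they are correlated and simulation is more realistic. Assumptions, none of them from the documents: 25 participants with one treatment and one control lesion each; paired two-sided t-tests on normal changes; assessor correlation 0.5-0.8; visit correlation 0.5-0.7; active-damage correlation 0-0.3; damage SD 0.5 or 1 times the active SD; total = active + damage. For 532 v 1064, between 6 and 18 participants are assumed to have both lasers. There were 16,000 trials per setting.

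| Choice left open | Tests | Chance of ≥1 false positive |
|---|---|---|
| None | 1 | 0.049-0.052 |
| The two section 3 hypotheses; one score, assessor and visit | 2 | 0.094-0.102 |
| Active CLASI v control at week 8; assessor open | 2 | 0.08-0.09 |
| Active CLASI v control; assessor and visit open | 2 × 2 = 4 | 0.126-0.168 |
| Three scores, both assessors, both visits, v control | 3 × 2 × 2 = 12 | 0.251-0.352 |

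Two tests that each hold 5% cannot exceed 2 × 0.05 = 10%, so the second row is read as about 10% and the excess as simulation error. Rounding the changes to whole points moves the last two maxima only to 0.170 and 0.362; that result depends on an assumed SD in points.

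The 12-test row assumes that the blinded observer scores all components. Section 7f lists limited CLASI among the items recorded on the two survey forms without saying which form, and the forms are not among the documents. The VAS is left out because the plan does not say it is rated per lesion.

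**The case against.** The best counter-argument is that a sensible reader can reconstruct the primary test. Section 7h pairs active CLASI with treatment against control, and section 7f calls the week 8 assessment final. On that reading only the assessor is open and the error rate is 8-9%, not 25-35%. This stands as a caution about size: the smaller figures are the better anchored in the text, and the larger ones need a less charitable reading. It does not supply an endpoint. The 7h rule is for suspension on harm, and the word final labels a visit without selecting it.

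A second objection is that a single-site study of 25, meant partly to inform further work, need not control error strictly across all comparisons. That is fair for the secondary comparisons, where an exploratory label with confidence intervals is legitimate. It does not excuse the primary one, because the protocol states hypotheses, a power calculation and a 0.05 level.

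Stronger readings are tempting but unsupported:
- **That the false-positive rate is 84%.** Three pairwise lesion contrasts would give 3 × 12 = 36 tests, and 1 − 0.95^36 = 0.84. That requires independence. At assumed common correlations of 0.5, 0.8 and 0.9 it is about 0.55, 0.27 and 0.18. Since the plan defines no family of tests, no percentage measures this trial's actual error rate.
- **That the in-person evaluator was unblinded.** The documents are silent on this.
- **That the endpoint was chosen after seeing results.** The reviews every 10 patients make this possible; nothing shows that it happened.

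**Conclusion.** The point holds and must be fixed. The primary-endpoint line is an end-of-participation rule, and no other text selects the efficacy score, assessor, visit and contrast. A positive result at 0.05 obtained by following this plan would not carry a 5% error rate and need not use the blinded assessment.

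The conclusion that the choice is open rests on the text alone. The sizes (about 10%; 13-17%, or 8-9% with week 8 fixed; and 25-35%) rest on the assumed correlations and, for the last, on the blinded observer scoring every component. The case for change does not need the largest figure: the two stated hypotheses alone roughly double the nominal rate.

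**What to change.** Replace the 7d line with one endpoint and one analysis. For example: limited active CLASI at Visit 3 (week 8), scored by the blinded photograph observer; within-participant difference between the first-assigned laser lesion (wavelengths pooled) and the control lesion, adjusted for their baseline difference; two-sided 0.05. The investigators may prefer another visit, since their hypothesis concerns speed, but must name one. In addition:

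- State that Visit 3 data are analysed as the week 8 outcome even when the visit was rescheduled or the second treatment was not given; section 7i allows both.
- Put 532 v control, 1064 v control and 532 v 1064 (the last in skin type I-III participants with both laser lesions) in a pre-stated order or under an adjustment, or label them exploratory with confidence intervals.
- Report in-person scores, damage and total CLASI, and VAS as supportive.
- Confirm that the Independent Observer Survey records active CLASI for each lesion at each visit.
- Fix the choice before outcome data are examined, or disclose it as post hoc.

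**Cost.** Wording and a form check. If the form lacks active CLASI, it can be scored from the photographs already taken at every assessment. The document is dated May 2019, after the October 2018 data-collection target, and actual progress is not stated. If outcomes have already been examined, disclosure is all that remains and it would not secure a 5% error rate.

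**Downsides.** Scale/hypertrophy may be harder to score from photographs. The pooled contrast does not show which wavelength works, and it depends on the skin-type mix because types IV-VI receive only 1064 nm. The fix addresses multiplicity and the choice of assessor only: the coin flip in section 7f picks the laser, no described randomization picks the control lesion, and bias from that choice remains.

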If participants miss study Visit 3, the researchers will attempt to reach the participant to reschedule. If the participant is unable to reschedule within 6 weeks of the missed appointment then the participant will be withdrawn from the study. Further data collection will not be continued.

8) Risks to participants

Laser treatment association risks^{15,16,19}:

Risks: >50%

- Pain/Discomfort – Additionally sharp burning/stinging pain can occasionally be felt.

Risks: <10%

- Redness/Swelling/Bruising – Short term redness (erythema) or swelling (edema) of the treated area is common and may occur. There also may be some bruising.
- Skin Color Changes – During the healing process, there is a possibility that the treated area may become either lighter (hypopigmentation) or darker (hyperpigmentation) in color compared to the surrounding skin. This is usually temporary, but, on a rare occasion, it may be permanent.
- Itching/Burning/Dry skin – Treatment may result in itching, burning, and/or dry skin during the recovery period.
- Red Rash/Bumps – Red rash/bumps may appear after treatment. This resolves with time.
- Acne flare-up or cold sore – this may occur after treatment.

Risks: <1%

- Wounds – Treatment can result in burning, blistering, scabbing, or bleeding of the treated areas.
- Infection – Infection is a possibility whenever the skin surface is disrupted, although proper self-wound care should prevent this.
- Scarring – Scarring is a rare occurrence, but it is a possibility when/if the skin surface is disrupted. To minimize the chances of scarring, it is important that participants follow all post-treatment instructions provided by the research staff. (see attached pre- and post-treatment instructions)

Other risks:

- Sun Exposure / Tanning Beds/ Artificial Tanning - May increase risk of side effects and adverse events and must be avoided.
- Eye Exposure – Protective eyewear (shields or goggles) will be provided to the participant during the treatment. Failure to wear protective eyewear during the entire treatment may cause severe and permanent eye damage.
- Lack of improvement (procedure may not work) or exacerbation of cutaneous lupus.

There is unknown risk to the an embryo or fetus should the participant be pregnant as none of the clinical trials with the laser were performed on pregnant women.

There are no risks to an embryo or fetus should the participant become pregnant.

There is no risk to non-participants.

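### The plan records no outcome for an adverse effect still present at Visit 3, so such a pigment change or scar cannot be classed as resolving or lasting

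*Combined protocol and SAP*

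**What the plan says.** Section 7(d) places an end-of-participation rule under the primary endpoints: "Participation in the study will end after the third visit". Section 7(e) adds a cap, "Each participant will be in the study for a maximum of 8 weeks", and the schedule: "The laser treatments will be spaced 4 weeks apart between visit 1 and visit 2", then "Finally, 4 weeks after visit 2, the participants will be followed up during visit 3". The study as a whole closes on the same terms: "The study will end when the last participant has completed the 2 laser treatments and follow up". None of these sentences makes an exception for an adverse effect that is still open.

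Section 7(d) lists among its secondary safety endpoints "Adverse reaction to the laser treatment such as blister, ulceration, and scarring". Section 7(f) adds hyperpigmentation and hypopigmentation to the effects monitored, and scores dyspigmentation in the limited CLASI only as absent or present, with nothing on duration. Section 8 puts colour change in its below-10% band and says "This is usually temporary, but, on a rare occasion, it may be permanent". Scarring is in the below-1% band. Section 4 expects such effects usually to fade in a few weeks and states no upper limit.

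Section 7(i) deals with a participant who misses Visit 3 and cannot rebook within 6 weeks: "then the participant will be withdrawn from the study. Further data collection will not be continued". Sections 6, 7(f) and 12 offer treatment or referral for research injuries, but tie no recording of outcomes to that care.

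**The concern.** The protocol treats scarring and pigment change as harms worth monitoring and acknowledges that pigment change may not reverse. Yet the last look comes 4 weeks after the second session, with nothing planned afterwards. If the plan is followed as written, a new change visible at that visit enters the dataset as present and never acquires an outcome.

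Two things are at stake. The first is what the safety data can support. Section 4 argues for laser partly on its mild side effects and hopes to encourage wider use. Whether a visible change goes away bears directly on that message. Pigment change is also the reason section 7(f) gives for restricting the 532 nm laser by skin type. The second is participant protection: someone with an open effect leaves the study with no planned check on how it ended. Section 11 also has the list linking names to study numbers destroyed at study completion, which makes later linkage harder.

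**Working it through.** **1. Reproduce the stated schedule (section 7(e)).** First session at week 0. Second session at 0 + 4 = week 4. Visit 3 at 4 + 4 = week 8, which matches the 8-week maximum. Follow-up is 8 − 4 = 4 weeks after the second session and 8 − 0 = 8 weeks after the first.

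**2. Apply the rescheduling rules (section 7(i)).** Visit 2 may be up to 2 weeks late, after which the second treatment is skipped. Visit 3 may be up to 6 weeks late.

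| Case | Last laser (week) | Visit 3 (week) | Gap (weeks) |
|---|---|---|---|
| On schedule | 4 | 8 | 4 |
| Visit 2 two weeks late, Visit 3 kept at week 8 | 6 | 8 | 2 |
| Visit 2 on time, Visit 3 six weeks late | 4 | 14 | 10 |
| Visit 2 two weeks late, Visit 3 timed from it and six weeks late | 6 | 16 | 10 |
| Second treatment skipped, Visit 3 on time | 0 | 8 | 8 |
| Second treatment skipped, Visit 3 six weeks late | 0 | 14 | 14 |

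The gap therefore runs from about 2 to 14 weeks, with 4 as the scheduled value. In every row there is one last observation and nothing after it. Visit 3 at week 14 or 16 also contradicts the 8-week maximum, so those passages need reconciling in any case.

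**3. What each pattern of observation supports.**
- Present at Visit 2, absent at Visit 3: temporary.
- Appears and resolves between visits, and is reported: temporary.
- Present at Visit 3, from either session: unclassified. Section 4 allows that it is still fading, section 8 allows that pigment change may be permanent, and no later observation separates the two.
- Known to be open, and Visit 3 missed beyond 6 weeks: unclassified, because data collection stops for that participant.

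**4. Size.** Inputs: N = 25 (section 7(a)) and the bands in section 8, read as per-participant upper bounds.
- Colour change of any duration: below 25 × 0.10 = 2.5 participants.
- Scarring: below 25 × 0.01 = 0.25 participants.
- If a share s of colour changes is still present at Visit 3, the expected number is below 2.5 × s. The documents do not give s. The range is 0 (s = 0) to 2.5 (s = 1).
- Taking the bounds as rates and participants as independent, the chance of at least one occurrence is 1 − 0.90^25 = 0.93 for colour change and 1 − 0.99^25 = 0.22 for scarring. These are ceilings for any occurrence, not for persistence.

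**5. What longer follow-up could not give.** Even with complete outcomes, 0 lasting cases in 25 leaves a one-sided 95% upper limit of 1 − 0.05^(1/25) = 11.3%. Follow-up would classify individual cases but would not estimate a precise rate.

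**The case against.** The best defence is that the schedule fits the protocol's own expectation. Effects usually fade within weeks, Visit 3 falls weeks after the last session, and the main aim is comparative efficacy, with no primary safety endpoint. First-session effects are seen at two later visits, over 8 weeks. Injuries are treated or referred, participants hold the investigators' contact details, and section 7(f) draws survey items partly from medical records. Dyspigmentation and scarring are also lupus damage items, so longer follow-up would not cleanly separate laser from disease. The surveys and the pre- and post-treatment instructions are attachments not in the text, so a provision there cannot be excluded.

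Much of this stands, and it limits the point. A reader might go further in four ways that the documents do not support:
- **That the trial cannot distinguish temporary from permanent change at all.** It can for anything seen to resolve. Only changes still present at the last assessment are unclassified.
- **That the protocol says follow-up stops despite an unresolved event.** No sentence says so. It follows from the flat end rule, the 8-week cap and the absence of an exception. The stop on data collection in 7(i) covers only those withdrawn for missing Visit 3, and section 7(g) keeps data already collected from participants who withdraw.
- **That there is a 93% chance of losing an outcome.** That figure is the ceiling for any colour change, including the usual temporary kind.
- **That routine care will not fill the gap.** Recruitment reaches beyond clinic patients, so it may not, but the documents do not show that those volunteers lack care.

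What the defence does not supply is a place where the outcome of an open effect would be recorded. Care after an injury is not data collection, and an expectation that effects usually fade does not classify one that has not.

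**Conclusion.** The point holds in this limited form: as the plan is written, pigment change or scarring still present at the last assessment has no recorded outcome and cannot be classed as resolving or lasting. It concerns at most a few of 25 participants. The exact number is unknown because no persistence rate is given. It does not touch any efficacy comparison, and it is a cheap improvement to the safety data rather than a flaw that undermines the trial.

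The conclusion rests on the flat end rule meaning what it says and on the unseen attachments containing no follow-up provision. The bound of 2.5 further assumes that the section 8 bands apply per participant.

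**What to change.** - **Sections 7(d) and 7(e):** add an exception to the end-of-participation rule and to the 8-week maximum. An adverse effect on a study lesion that is unresolved at Visit 3 has its outcome recorded, by photograph or contact and with the participant's consent, until it is resolved, stable, or recorded as persisting at a stated cut-off date. Say that study completion, and so destruction of the linking list under section 11, waits for that date.
- **Section 7(i):** allow a participant withdrawn for missing Visit 3 who has a known open adverse effect to be contacted for its outcome, with consent. Reconcile the rescheduling limits with the 8-week maximum in the same edit.
- **Unchanged:** efficacy assessment still ends at Visit 3, and no treatment is altered.

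The cost is a small protocol and consent amendment, extra contact with a few participants at most, and a slightly later close for those cases. Attribution to laser rather than lupus damage will remain imperfect, and no precise rate of lasting harm can come from 25 participants.
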